We advise all participants that they are under no obligation to respond to our questions and may decline to answer or stop at any time. Should a participant experience fatigue, we will allow them to take a break and continue or schedule another time within the next 48 hours to complete remaining questionnaires. If a subject responds to the symptom questionnaires that they have often or always felt depressed and/or hopeless in the past 7 days the researchers will refer them to their Primary Care Provider and provide a list of mental health resources including the Boys Town Grief Hotline. If upon questioning as to whether they have any plans to hurt themselves, they respond with a "yes" they will be immediately escorted to the Emergency Department or 9-1-1 will be contacted on their behalf.

Minimization of Risk of Exercise:

All participants will have successfully completed a cardiopulmonary exercise test (CPET). The results from the CPET will be used to develop an individualized exercise prescription for each participant that will guide heart rate parameters during exercise. Participants will be taught to monitor the intensity of their exercise by using heart rate and the rating of perceived exertion from their participation in our study orientation. We reduce the risk of exercising at home by requiring that another adult be present during the exercise in the event a subject experiences an adverse event requiring medical attention. The other adult will be instructed to contact the provider if the participant experiences a non-emergent adverse event or initiate local EMS, in the event of an emergency. The other adult will be instructed to then follow the instructions of the dispatcher. A list of potential adverse events that would warrant a call to a provider or EMS was attached to the application and will be shared with all participants. It is important to note that 150 minutes of moderate-intensity exercise is recommended for these patients and HFrEF patients are not eligible for cardiac rehabilitation. If these patients were not participating in this study, they could be doing this exercise on their own without the guidance that results from participating in this study.

Minimization of Risk of Loss of Confidentiality:

To protect against possible risks to confidentiality, research data will be stored in a locked

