8.3 ADVERSE EVENTS AND SERIOUS ADVERSE EVENTS

8.3.1 DEFINITION OF ADVERSE EVENTS

This protocol uses the definition of adverse event from 21 CFR 312.32 (a): any untoward medical occurrence associated with the use of an intervention in humans, ***whether or not considered intervention-related.***

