8.3.3.2 RELATIONSHIP TO STUDY INTERVENTION/EXPERIMENTAL MANIPULATION

All adverse events (AEs) will have their relationship to study procedures, including the intervention, assessed by an appropriately-trained clinician based on temporal relationship and his/her clinical judgment. The degree of certainty about causality will be graded using the categories below.

- **Related** – The AE is known to occur with the study procedures, there is a reasonable possibility that the study procedures caused the AE, or there is a temporal relationship between the study procedures and the event. Reasonable possibility means that there is evidence to suggest a causal relationship between the study procedures and the AE.
- **Not Related** – There is not a reasonable possibility that the study procedures caused the event, there is no temporal relationship between the study procedures and event onset, or an alternate etiology has been established.

OR

- **Definitely Related** – There is clear evidence to suggest a causal relationship, and other possible contributing factors can be ruled out. The clinical event, including an abnormal laboratory test result, occurs in a plausible time relationship to study procedures administration and cannot be explained by concurrent disease or other drugs or chemicals. The response to withdrawal of the study procedures should be clinically plausible. The event must be pharmacologically or phenomenologically definitive.
- **Probably Related** – There is evidence to suggest a causal relationship, and the influence of other factors is unlikely. The clinical event, including an abnormal laboratory test result, occurs within a reasonable time after administration of the study procedures, is unlikely to be attributed to

concurrent disease or other drugs or chemicals, and follows a clinically reasonable response on withdrawal.

- **Potentially Related** – There is some evidence to suggest a causal relationship (e.g., the event occurred within a reasonable time after administration of study procedures). However, other factors may have contributed to the event (e.g., the participant's clinical condition, other concomitant events). Although an AE may rate only as "possibly related" soon after discovery, it can be flagged as requiring more information and later be upgraded to "probably related" or "definitely related", as appropriate.

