8.3.4 TIME PERIOD AND FREQUENCY FOR EVENT ASSESSMENT AND FOLLOW -UP

[The occurrence of an adverse event (AE) or serious adverse event (SAE) may come to the attention of study personnel during study visits and interviews of a study participant presenting for medical care, or upon review by a study monitor.

All AEs, not otherwise precluded per the protocol, will be captured on the appropriate case report form (CRF). Information to be collected includes event description, time of onset, clinician's assessment of severity, relationship to study procedures (assessed only by those with the training and authority to make a diagnosis), and time of resolution/stabilization of the event. All AEs occurring while on study will be documented appropriately regardless of relationship. All AEs will be followed to adequate resolution.

Any medical or psychiatric condition that is present at the time that the participant is screened will be considered as baseline and not reported as an AE. However, if the study participant's condition deteriorates at any time during the study, it will be recorded as an AE.

Changes in the severity of an AE will be documented to allow an assessment of the duration of the event at each level of severity to be performed. Documentation of onset and duration of each episode will be maintained for AEs characterized as intermittent.

<Insert role or name> will record events with start dates occurring any time after informed consent is obtained until 7 (for non-serious AEs) or 30 days (for SAEs) after the last day of study participation. At each study visit, the investigator will inquire about the occurrence of AE/SAEs since the last visit. Events will be followed for outcome information until resolution or stabilization.

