8.3.5 ADVERSE EVENT REPORTING

The study will be stopped if any adverse events result in the necessity for emergency care. These events will be reported immediately to the IRB and closely investigated by study personnel. If any death occurs as the result of exercise or within 3 hours of an exercise session, the study will be stopped.

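### One adverse event needing emergency care, in either arm and related or not, stops the whole study, and the rule does not say whether that means a pause or termination

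*Combined protocol and SAP*

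**What the plan says.** The rule appears in the same words in 8.3.2 and 8.3.5: "The study will be stopped if any adverse events result in the necessity for emergency care". The next sentence adds: "These events will be reported immediately to the IRB and closely investigated by study personnel". The death rule follows: "If any death occurs as the result of exercise or within 3 hours of an exercise session, the study will be stopped".

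The events that can meet the trigger are defined broadly. Section 8.3.1 counts an adverse event "whether or not considered intervention-related". Section 8.3.4 says "All AEs occurring while on study will be documented appropriately regardless of relationship", with recording from consent "until 7 (for non-serious AEs) or 30 days (for SAEs) after the last day of study participation".

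Section 10.1.2 is the general section on suspension and closure. It allows temporary suspension or premature termination, says that the study may resume once safety, compliance and data-quality concerns are addressed, and lists the bodies to be satisfied. It does not mention the emergency-care rule, and 8.3.2 and 8.3.5 do not mention it.

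Three other entries bear on a repair. Section 8.3.3.2 prints a two-level and a five-level relatedness scale as alternatives. Oversight is a single safety monitor in 8.1 but a DSMB or safety committee in 10.1.6. Section 9.4.4 (Safety Analyses) reads N/A.

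**The concern.** The threshold is one event, with no condition on cause, arm or expectedness. A control participant's emergency visit for something unconnected with exercise would halt everyone. A death unrelated to exercise and outside the 3-hour window would not meet the death rule. The less grave outcome therefore has the wider trigger, and no reason is given.

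The rule also leaves its own consequence open. If the stop is lasting, it cuts short the Week 12 and Week 24 feasibility data, which are the primary purpose (Section 3). If it is a pause, the rule itself names nobody to review it and does not say whether follow-up visits continue meanwhile.

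A larger trial would need emergency-care counts by arm to set its own stopping rule, and no such summary is planned.

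**Working it through.** **Does an unrelated event meet the trigger?** Set the texts side by side.

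- Emergency-care rule (8.3.2, 8.3.5): any adverse event needing emergency care; no limit on cause or timing.
- Definition and capture (8.3.1, 8.3.4): relatedness is not required.
- Death rule (same paragraph): limited to exercise as cause, or to 3 hours around a session.

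The answer is yes, in either arm.

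**How easily is it met?** The plan states no event rate or stopping probability, so there is no figure to reproduce. Inputs from the documents: N = 25 (1.1), 1:1 allocation (6.3), 24 weeks of follow-up (4.4). The per-participant risk p of at least one emergency-care event over 24 weeks is an assumption. Participants are taken as independent.

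P(at least one trigger) = 1 − (1 − p)^N

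| Assumed p | N = 25 |
|---|---|
| 1% | 22.2% |
| 2% | 39.7% |
| 5% | 72.3% |
| 10% | 92.8% |

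Break-even: p = 1 − 0.5^(1/25) = 0.0273, or 2.7%. As a rate, exposure is 25 × 168/365.25 = 11.50 person-years, and ln 2 / 11.50 = 0.060 events per person-year. Below that, the study more often finishes than triggers.

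Two variations on the break-even:

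- If only intervention-arm events counted (12.5 people on average): 1 − 0.5^(1/12.5) = 5.4%.
- Section 6.1.1 gives n = 25 for the intervention. If the total were 50: 1 − 0.5^(1/50) = 1.4%.

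**What would be lost?** Nothing need be lost under a pause with follow-up continuing. Under a permanent stop, further assume 25 entries evenly spaced over 18 months, full retention and no data after the stop. The expected number reaching a visit is the sum over participants of exp(−rate × total exposure accrued by everyone when that participant reaches the visit).

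| Assumed rate per person-year | Reach Week 12 | Reach Week 24 |
|---|---|---|
| 0.02 | 22.3 | 21.7 |
| 0.05 | 19.0 | 17.6 |
| 0.1 | 14.8 | 12.7 |
| 0.2 | 9.7 | 7.0 |

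No stopping chance is given for the repaired rule. It would need the share of events judged related and the share falling within 3 hours of exercise, and the documents give neither.

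**The case against.** The strongest defence is that the breadth is deliberate. Participants exercise at home with only another adult present, and data collectors are unblinded (6.3). A trigger that does not wait for a relatedness judgement has a real safety rationale. This stands as a reason for a low threshold and for halting on any plausible causal link. It does not explain why a plainly unrelated event must halt the study, nor why the death rule is narrower.

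The second defence is that 10.1.2 already covers the pause: it gives a basis for resuming and lists who must be satisfied. Investigation of each event under 8.3.5 fits a sequence of halt, review and decision. Much of this stands. The gap is a missing definition and cross-reference, not a missing process. A reader might infer that 8.3.5 contradicts 10.1.2, or that it requires termination; the texts support neither.

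A reader might also infer conflict with 2.3.3, where the other adult is to "initiate local EMS, in the event of an emergency", and with 6.1.1, where a participant who relapses after hospitalisation returns to weekly coaching. Caring for one person and halting the study are compatible, and a hospital stay need not be an emergency, so these sections add little.

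Finally, 9.4.4 might be read as meaning that emergency-care counts will go unreported. That is too strong: adverse events are recorded on CRFs (8.3.4), and 10.1.11 commits to submitting and publishing results. What is missing is a planned by-arm summary.

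**Conclusion.** The point holds and should be fixed. As written, one emergency-care event unrelated to exercise or study procedures, in either arm, stops a 25-person feasibility trial, and the rule does not say for how long. That much rests on the text alone.

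The size depends on an event rate the documents do not give. The compact result is the break-even: about 2.7% risk per participant over 24 weeks with N = 25. A reader might take this to mean that the trial will probably be stopped; without a rate, that does not follow. The loss of Week 12 and Week 24 data also depends on the stop being lasting, which the text leaves open.

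**What to change.** In 8.3.2 and 8.3.5:

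1. Apply the automatic halt to emergency-care events judged Potentially, Probably or Definitely Related on the five-level scale in 8.3.3.2, or starting within 3 hours of an exercise session. Use the five-level scale, because on the two-level scale it is enough for Related that "there is a temporal relationship between the study procedures and the event". Events judged Unlikely or Not Related are still reported immediately to the IRB and investigated, without an automatic halt.
2. State that the stop, for this rule and for the exercise-death rule, means a pause of enrolment and exercise, with follow-up data collection continuing where safe. One safety body, chosen between 8.1 and 10.1.6, reviews it; the study then resumes or terminates under 10.1.2.

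Separately, in 9.4.4 replace N/A with counts and proportions of participants with adverse events and with emergency-care events, by randomised arm. This fits the descriptive plan in 9.4.1.

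The cost is mostly wording and one table. One CRF item is needed: the time of the last exercise session for each emergency-care event. Section 8.3.4 lists event onset but not session time; heart-rate monitor data may supply it. The downside is that an emergency wrongly judged unrelated and outside the 3-hour window would not trigger an automatic pause.

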8.3.6 SERIOUS ADVERSE EVENT REPORTING

In consultation with the PI, a trained member of the study team will be responsible for conducting an evaluation of a serious adverse event and shall report the results of such evaluation to the NIH and the reviewing Institutional Review Board (IRB) as soon as possible, but in no event later than 10 working days after the investigator first learns of the event.

8.3.7 REPORTING EVENTS TO PARTICIPANTS

N/A

8.3.8 EVENTS OF SPECIAL INTEREST

N/A

8.3.9 REPORTING OF PREGNANCY

There are no interventions that are likely to be of risk to a fetus. Pregnancy is unlikely in our patient population.

8.4 UNANTICIPATED PROBLEMS

8.4.1 DEFINITION OF UNANTICIPATED PROBLEMS

This protocol uses the definition of Unanticipated Problems as defined by the Office for Human Research Protections (OHRP). OHRP considers unanticipated problems involving risks to participants or others to include, in general, any incident, experience, or outcome that meets all of the following criteria:

- Unexpected in terms of nature, severity, or frequency given (a) the research procedures that are described in the protocol-related documents, such as the Institutional Review Board (IRB)-approved research protocol and informed consent document; and (b) the characteristics of the participant population being studied;
- Related or possibly related to participation in the research (“possibly related” means there is a reasonable possibility that the incident, experience, or outcome may have been caused by the procedures involved in the research); and
- Suggests that the research places participants or others at a greater risk of harm (including physical, psychological, economic, or social harm) than was previously known or recognized.]

8.4.2 UNANTICIPATED PROBLEMS REPORTING

The investigator will report unanticipated problems (UPs) to the reviewing Institutional Review Board (IRB) and to the Data Coordinating Center (DCC)/lead principal investigator (PI). The UP report will include the following information:

- Protocol identifying information: protocol title and number, PI's name, and the IRB project number
- A detailed description of the event, incident, experience, or outcome
- An explanation of the basis for determining that the event, incident, experience, or outcome represents an UP
- A description of any changes to the protocol or other corrective actions that have been taken or are proposed in response to the UP

To satisfy the requirement for prompt reporting, UPs will be reported using the following timeline:

- UPs that are serious adverse events (SAEs) will be reported to the IRB and to the DCC/study sponsor/funding agency within <insert timeline in accordance with policy> of the investigator becoming aware of the event
- Any other UP will be reported to the IRB and to the DCC/study sponsor/funding agency within <insert timeline in accordance with policy> of the investigator becoming aware of the problem
- All UPs should be reported to appropriate institutional officials (as required by an institution's written reporting procedures), the supporting agency head (or designee), and the Office for Human Research Protections (OHRP) within <insert timeline in accordance with policy> of the IRB's receipt of the report of the problem from the investigator

8.4.3 REPORTING UNANTICIPATED PROBLEMS TO PARTICIPANTS

N/A

9 STATISTICAL CONSIDERATIONS

9.1 STATISTICAL HYPOTHESES

We do not have a separate statistical plan for this pilot study.

- Primary Endpoint(s): Feasibility and acceptability
- Secondary Endpoint(s): Exercise, symptoms, quality of life

9.2 SAMPLE SIZE DETERMINATION

Sample size was determined on the basis of what we expect to recruit vs. a formal power calculation given the pilot nature of this study.

9.3 POPULATIONS FOR ANALYSES

We will not be completing inferential analyses.

9.4 STATISTICAL ANALYSES

9.4.1 GENERAL APPROACH

We will report descriptive statistics including counts, proportions, and means only.

9.4.2 ANALYSIS OF THE PRIMARY ENDPOINT(S)

- *We will describe feasibility and acceptability.*

9.4.3 ANALYSIS OF THE SECONDARY ENDPOINT(S)

Descriptive statistics will be calculated as appropriate.

9.4.4 SAFETY ANALYSES

N/A

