4.4 END-OF-STUDY DEFINITION

The end of the study is defined as completion of the 24 week follow-up assessment shown in the Schedule of Activities (SoA), **Section 1.3**.

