6.1.1 STUDY INTERVENTION

The HEART Camp Connect intervention is founded in social-cognitive theory⁴⁶ and the future-oriented motivation and self-regulation model proposed by Miller and Brickman.⁴⁷ HEART Camp Connect (n=25) includes weekly virtual coaching sessions with experienced coaches from Engage. For 3 weeks per month, coaches and participants meet 1-on-1 via videoconference to review heart rate data, exercise diaries from the prior week and initiate discussion related to behavioral change mechanisms. One week per month HEART Camp Connect participants will be assigned to a small group (1 coach:5 participants) exercise/observation session. During these sessions, coaches will demonstrate exercises and observe participants via videoconference for proper form and real-time encouragement in a group setting. Coaches will call any HEART Camp Connect participant that fails to

attend their scheduled weekly coaching session for 2 consecutive weeks. Participants achieving a minimum of 120 minutes of moderate-intensity exercise per week on average weeks 1-12 will be given the option to opt-out of coaching sessions for weeks 13-16. We recognize that this could potentially create variation in the dose of the coaching and therefore, will closely monitor the minutes of coaching per participant throughout the study. We will also closely monitor adherence during this time. Participants that relapse (become non-adherent for 2 consecutive weeks) for any reason (e.g., hospitalization, loss of motivation) will return to weekly coaching for the remainder of the intervention. Testing optional coaching is part of our feasibility assessment and increases the future scalability of this intervention. In the sustainability period (Weeks 17-24), weekly coaching stops, and HEART Camp Connect participants are expected to self-regulate exercise and maintain adherence.

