8.3.2 DEFINITION OF SERIOUS ADVERSE EVENTS

The study will be stopped if any adverse events result in the necessity for emergency care. These events will be reported immediately to the IRB and closely investigated by study

personnel. If any death occurs as the result of exercise or within 3 hours of an exercise session, the study will be stopped.

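### Section 9.4.4 plans no safety summary, although adverse events are recorded in all participants and can stop the study; a descriptive by-arm table that records how each event was first found would close the gap

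*Combined protocol and SAP*

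**What the plan says.** The only entry under "9.4.4 SAFETY ANALYSES" is N/A. Section 9.1 states that the pilot has no separate statistical plan, so the summary is not deferred to another document. The general approach in Section 9.4.1 reads "We will report descriptive statistics including counts, proportions, and means only", and Section 9.3 adds "We will not be completing inferential analyses". Nothing in Section 9 mentions adverse events or a safety population.

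The rest of the protocol treats safety data as important:

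- Section 2.3.1 lists arrhythmia and death among the risks of exercise.
- The schedule in Section 1.3 has adverse event reporting at Weeks 0, 12 and 24, with no distinction by arm.
- Section 8.3.4 records all events whatever their relationship to the study, and says "At each study visit, the investigator will inquire about the occurrence of AE/SAEs since the last visit".
- Sections 8.3.2 and 8.3.5 both say "The study will be stopped if any adverse events result in the necessity for emergency care".

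Two further provisions bear on how events are found. Section 6.1.1 says the intervention "includes weekly virtual coaching sessions", while no contact schedule is given for enhanced usual care. Section 6.3 says data collectors are not blinded. As to timing, events are recorded "until 7 (for non-serious AEs) or 30 days (for SAEs) after the last day of study participation", while Section 4.4 defines the end of the study as "completion of the 24 week follow-up assessment".

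**The concern.** Data serious enough to stop the study have no planned summary. Section 4.2 gives support for a larger trial as the reason for this one, and whoever plans that trial will need to know how many participants in each arm had an event. If nothing is specified, the counts will be left out or put together after the fact.

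Counts put together after the fact could mislead. Coaches speak to one arm nearly every week, and Section 6.1.1 mentions hospitalization as a reason for relapse that brings a participant back to weekly coaching. Coaches may therefore learn of events that a participant would not recall at a visit 12 weeks later. Controls have no comparable contact described. The items listed for the case report form in Section 8.3.4 do not include how an event came to light, so a true excess could not later be told apart from extra detection. That information is hard to reconstruct and has to be collected as events occur.

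**Working it through.** The plan gives no safety figure to reproduce. The checks below show what the gap and the uneven contact could amount to.

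**1. Contacts after baseline**

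- Both arms: 2 scheduled visits, Weeks 12 and 24 (Section 1.3).
- Coaching arm: weekly sessions in Weeks 1 to 16, with Weeks 13 to 16 optional for some participants (Section 6.1.1), so 12 to 16 sessions if all are attended.
- Totals: 12 + 2 = 14 to 16 + 2 = 18 in the coaching arm, against 2 scheduled for controls.
- Ratio of contacts: 14/2 = 7 to 18/2 = 9.

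This counts contacts only. It is not a ratio of detection, because the question at each visit covers the whole interval since the last visit in both arms.

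**2. What uneven contact could do to the counts**

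Suppose true event rates are equal. Let r be the share of events captured at study visits, the same in both arms, and w the share of the missed events that coaches pick up. The documents give neither, so both are assumptions. The apparent ratio of coaching to control events is [r + (1 − r)w] / r.

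| r | w = 0 | w = 0.3 | w = 0.9 |
|---|---|---|---|
| 0.5 | 1.0 | (0.5 + 0.15)/0.5 = 1.30 | (0.5 + 0.45)/0.5 = 1.90 |
| 0.7 | 1.0 | (0.7 + 0.09)/0.7 = 1.13 | (0.7 + 0.27)/0.7 = 1.39 |
| 0.9 | 1.0 | (0.9 + 0.03)/0.9 = 1.03 | (0.9 + 0.09)/0.9 = 1.10 |

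The distortion is nil if coaches pass nothing on, slight if visits capture most events, and large only if visits miss about half.

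**3. What a zero count would show**

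With 0 events in n participants, the two-sided exact 95% upper limit is 1 − 0.025^(1/n).

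- The Synopsis enrols 25 in total, and Section 6.3 randomizes 1:1, so the larger arm has about 13: 1 − 0.025^(1/13) = 24.7%.
- Section 6.1.1 writes n=25 for the coaching arm: 1 − 0.025^(1/25) = 13.7%.

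The two sample sizes do not agree. Either way, an empty row would not show that events are rare.

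**4. The window for serious events**

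Week 24 is day 168. Taking the Week 24 visit as the last day of participation, serious events are recorded to day 168 + 30 = 198, and no contact is scheduled after day 168. That is 30/198 = 15% of the recording window in days. It says nothing about how many serious events would be missed.

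**The case against.** This is a small pilot with a deliberately descriptive plan. Adverse events are still recorded on case report forms, serious events are evaluated and reported under Section 8.3.6, and Section 10.1.6 provides for safety oversight. That stands as far as it goes: safety information will exist, and what is missing is a planned summary. But a by-arm count is itself descriptive and fits Section 9.4.1, so the pilot label does not explain the N/A.

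A reader might infer that weekly coaching will find more events, that any count must therefore favour control, or that detection is 7 to 9 times as likely in the coaching arm. The documents do not support these readings. Section 8.3.4 names study visits, participants presenting for care, and monitor review as the routes by which events come to attention. It does not list coaching sessions, and no section tells coaches to report events. Visit enquiry covers the full interval in both arms. Section 2.3.3 gives all participants the list of events that warrant a call for help, and Section 8.1 sets data monitoring at least weekly without distinguishing arms. Contact in enhanced usual care is undescribed rather than known to be absent. Unequal detection is least plausible for emergency-care events and deaths. Only possible bias, of unknown size, can be claimed.

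Splitting events by source could also create the opposite bias. If an event that a coach reports in Week 5 is filed only under coach report, it drops out of the comparison and the coaching arm is undercounted. That objection is sound, and the fix needs a rule for events found by both routes.

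Confidence intervals go beyond Section 9.4.1 as written. For emergency-care events in particular, a fixed-n interval fits poorly, because such an event stops the study. Intervals are therefore optional.

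Finally, a recording window that runs past the last visit does not contradict the end-of-study definition. This too is right. What is missing is a statement of how events in that window will be found.

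**Conclusion.** The gap is real. Followed as written, the plan produces no safety summary from data collected in every participant and serious enough to stop the study. This rests on the text alone and needs no assumption.

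The second part is weaker. Described contact is one-sided, data collectors are unblinded and the source of a report is not recorded, so events could be found more often under coaching. The apparent ratio of 1.0 to about 1.9 depends wholly on the assumed capture rates and is an illustration, not an estimate.

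The serious-event window is a minor, separate omission. The upper limits of about 25% and 14% depend on which sample size is meant. The plan should be changed, but nothing here affects the sample size, the intervention or the stopping rule.

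**What to change.** 1. Replace N/A in Section 9.4.4 with a descriptive table by assigned arm: number and proportion of participants with at least one adverse event, serious adverse event, event related to study procedures, and emergency-care event. Section 8.3.3.2 offers two causality scales joined by OR; state which defines the related row.
2. Add a case report form field for how each event was first found: scheduled visit, coach contact, spontaneous report or record review. Add an emergency-care item if the form has none, since Section 8.3.4 does not list one.
3. Base the between-arm comparison on all events reported in answer to the same question at Weeks 12 and 24, including those a coach had already reported. List events known only through coaches separately. Make no between-arm test. This reduces uneven detection but may not remove it, since coaching could prompt recall and collectors are unblinded.
4. Treat exact 95% intervals as optional. If they are wanted, amend Section 9.4.1, and first reconcile the sample sizes in the Synopsis and Section 6.1.1.
5. State in Section 8.3.4 how serious events in the 30 days after last participation will be found, for example by record review.

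The cost is one or two extra fields, a few sentences of protocol text and one small table. The downside is that the table will be imprecise, and it should be labelled so.
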